**8.5.2. Drug and Alcohol Use Assessment.**

**8.5.2.a. Urine Screens.** The primary outcome measure will be cannabis use, as measured by twice-weekly quantitative urine screens during treatment. Cannabis is a particularly challenging drug of abuse for measuring outcome because of the *false-positive* urine screens that can occur as the result of long-term accumulation of cannabis metabolites. In an attempt to avoid false-positive results, we will obtain 2 supervised urine samples weekly: 1 at the medical visit and 1 on another day, ordinarily with 3-4 days separation from the clinical visits (e.g., Monday-Thursday, Tuesday-Friday, or Monday-Friday); this should maximize the time frame covered by our urine screens. We will send the urine samples to Quest Diagnostics Laboratory (Cambridge, MA, a NIDA-certified laboratory), where the urines will be screened by immunoassay for the THC metabolite 11-nor-carboxy- $\Delta$  9-tetrahydrocannabinol (THC-COOH) as well as other drugs of abuse. Urine creatinine concentrations will also be measured to assess urine concentration. The threshold for detection of THC-COOH will be 20 ng/ml. Samples positive for this metabolite will undergo further analysis by gas chromatography-mass spectroscopy to obtain quantitative THC-COOH concentration; we will then calculate the ratio of this metabolite to urine creatinine concentration. We will adopt the method of Heustis and Cone (1998) to differentiate new marijuana use from residual drug excretion as a result of previous use; these recommendations are based on their controlled clinical studies of urinary excretion profiles of creatinine and marijuana metabolites following marijuana administration in humans. We will label a urine negative (i.e., abstinent from cannabis) if 1) the ratio of THC-COOH to creatinine in the urine does not increase by >50% from the ratio obtained in the previous urine screen, and 2) the participant also reports using no cannabis since the previous urine test.

**McLean Hospital Application to the Institutional Review Board (IRB)  
Nabilone for Cannabis Dependence Detailed Protocol**

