**8.5.2.c. Other Drug and Alcohol Use Assessment.** Severity of cannabis and other substance use and its associated problems will be assessed at baseline and weeks 4, 10, and 14 with the Addiction Severity Index (ASI, 5th edition) (McLellan et al. 1992), a widely-used and independently-validated interview that measures the severity of problems in 7 areas of functioning that are frequently affected in patients with SUDs: drug use, alcohol use, employment, legal status, medical condition, social functioning, and psychological status. In addition to our primary focus on cannabis use (urine screens plus days of use), we will examine other substance use (using urine screens plus days of other substance use). We will use this method to determine the number of days of cannabis use and of any substance use (and conversely, days of abstinence). We will examine ASI composite scores as secondary measures of substance use outcome. We will also use the self-administered Drug and Alcohol Use Questionnaire. This measure, administered at baseline, addresses the context of lifetime and recent drug and alcohol use, as well as sociodemographic data. At each treatment visit, patients will complete a brief Weekly Drug and Alcohol Use Inventory, indicating their number of days using marijuana, other drugs, and alcohol during the previous week. The Marijuana Goals Questionnaire (Griffin et al. 1989) is a brief questionnaire administered at baseline to assess treatment goals, specifically, whether a participant is seeking abstinence or reduction in cannabis use. A 12-item self-administered questionnaire, the Marijuana Craving Questionnaire (MCQ), will be used to assess craving at baseline and weekly during treatment and at the 14-week follow-up visit (Heishman et al. 2009). A short form of the Marijuana Withdrawal Checklist (MWC) will be used to assess withdrawal symptoms at baseline and weekly during treatment and at the 14-week follow-up visit (Budney et al. 1999). If there is a discrepancy among results obtained by these methods of substance use assessment, we will meet with the participant and have a conversation about their substance use. After the conversation, we will use our clinical judgment to determine the level of use that we believe is most accurate for that participant. A new 6-page questionnaire that we created, the Marijuana Perceptions of Risk and Experiences Questionnaire (MPRE), will be distributed at baseline, and once during weeks 4, 10 and 14 to assess each participant's perceptions of cannabis risk/harm and his or her motivations to quit/continue using cannabis throughout the course of treatment.

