
**8.5.3. Mood and Impulsivity Assessments.** We will monitor participants' mood throughout the study using 3 assessments. The Beck Anxiety Inventory (BAI) is a 21-

**McLean Hospital Application to the Institutional Review Board (IRB)  
Nabilone for Cannabis Dependence Detailed Protocol**

item self-report measure that can be used to assess the severity of anxiety. The Quick Inventory of Depressive Symptomatology (QIDS-SR) is a short self-report questionnaire for depressive symptoms used successfully in the STAR\*D project. The Positive and Negative Affect Scale (PANAS) is a 20-item self-report scale in which mood variables are rated by participants on a 1-5 scale. The Barratt Impulsiveness Scale (BIS-11) is a commonly used tool to measure impulsivity in various neuropsychological disorders as well as in substance abuse. Three dimensions can be assessed using this scale, which include Cognitive Impulsivity, Motor Impulsivity, and Non-planning Impulsivity.

**Table 8.1** Schedule of Measures

Measure	Baseline	Weekly	Weeks 4 &10	Week 14
Diagnostic Assessment				
1. Structured Clinical Interview for DSM-IV a	X			
Drug and Alcohol Assessment				
2. Quantitative Urine Toxicological Analysis b	X	X b	X	X
3. Addiction Severity Index	X		X	X
4. Drug and Alcohol Use Questionnaire	X			
5. Weekly Drug and Alcohol Use Inventory	X	X	X	X
6. Marijuana Goals Questionnaire	X			
7. Marijuana Craving Questionnaire	X	X	X	X
8. Marijuana Withdrawal Checklist	X	X	X	X
9. Marijuana Perceptions of Risk and Experiences	X		X	X
Mood and Impulsivity Assessment				
10. Quick Inventory of Depressive Symptomatology	X		X	X
11. Beck Anxiety Inventory	X		X	X
12. Positive and Negative Affect Scale	X		X	X
13. Barratt Impulsiveness Scale	X		X	X
Medical & Safety Assessment (medical visits)				
14. Physical examination	X			X
15. ECG	X			X
16. Urine pregnancy test	X		X	X
17. Laboratory tests c	X			X
18. Adverse Events & Side Effects	X	X		X
19. Columbia Suicide Severity Rating Scale	X	X	X	X

aFull SCID at baseline

bTwice a week during treatment;

cTests include urinalysis, liver function tests, electrolytes, complete blood count, & blood chemistries

**8.6. Medication Adherence Assessment.** The proposed studies involve chronic administration of medication given under double-blind conditions. Three methods of

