**8.9. Statistical Analysis**

The primary data analysis will be an intent-to-treat analysis, which includes all randomized participants. Of note, every attempt will be made to continue assessing participants even if they drop out of treatment. In addition, we will replicate all analyses with the completers only. The primary and secondary outcome variables are intended to explore various aspects of response to therapy and to help define a clinically meaningful response. The primary outcome measures, Actiwatch-scores, daily diaries, TLFB self-report data, in addition to quantitative urinary THC metabolites, have been chosen for their ability to indicate daily use of cannabis by relying on self-report of use.

Specifically, for assessing the effect of nabilone on cannabis use patterns, we propose to use the generalized estimating equations (GEE) approach to longitudinal analysis, appropriately accounting for the positive correlation among repeated urine screen assessments within the same individual.

Analyses of secondary substance use outcomes will focus on the number of days of cannabis use and of any substance use (and conversely, days of abstinence) during treatment and post-treatment follow-up. In addition, we will also examine the ASI Drug and Alcohol composite scores. Frequency of days of cannabis use (and any substance use and days of abstinence) will be analyzed via a log-linear (or Poisson) regression model, controlling for pre-treatment frequency of days of cannabis use. Although log-linear regression methods are considered appropriate for the analysis of count or frequency data, in many biomedical applications, count data have variability that far exceeds that predicted by the Poisson distribution; we expect that days of cannabis use (and any substance use and days of abstinence) will not be an exception. Linear mixed effects models will be used to examine the effect of treatment group on changes in the ASI Drug and Alcohol composite scores during treatment and post-treatment follow-up assessments (as determined by the group-by-time interaction in the linear mixed effects regression models). The linear mixed effects model will include random intercepts and slopes to appropriately account for correlation among repeated measures and heterogeneity of variance over time; the model will be fit using PROC MIXED in SAS.

**McLean Hospital Application to the Institutional Review Board (IRB)  
Nabilone for Cannabis Dependence Detailed Protocol**

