In secondary analyses of mood outcomes, mood episodes will be assessed during treatment and post-treatment follow-up, using the QIDS, BAI, and PANAS; changes in risk of mood episodes during treatment and post-treatment follow-up assessments will be analyzed via a logistic regression model (similar to the logistic model above) that will be fit using the GEE approach (as implemented in PROC GENMOD in SAS) to account for correlation among repeated binary outcomes on the same individual. To examine the effect of nabilone on changes in risk for mood episodes during treatment and post-treatment follow-up, the logistic regression model will include the effects of treatment condition and the baseline measure of the outcome.

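### The count model for days of any substance use adjusts only for pre-treatment cannabis days and leaves out the baseline alcohol and other-drug use that the trial already records

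*Combined protocol and SAP*

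**What the plan says.** Section 8.9 lists as secondary substance-use outcomes the "number of days of cannabis use and of any substance use (and conversely, days of abstinence", during treatment and follow-up. One sentence sets the model for all three counts. Its subject is "Frequency of days of cannabis use (and any substance use and days of abstinence", and these "will be analyzed via a log-linear (or Poisson) regression model, controlling for pre-treatment frequency of days of cannabis use". No other covariate is named there, and no other section adds a baseline measure of alcohol or other drugs to these models.

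Abstinence is introduced only as the converse of the use-day counts; the section does not say from which substance. For urine screens, section 8.5.2.a uses the term for cannabis alone: "We will label a urine negative (i.e., abstinent from cannabis".

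For the mood outcomes, section 8.9 takes a different approach: "the logistic regression model will include the effects of treatment condition and the baseline measure of the outcome".

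Baseline information on other substances exists. Section 8.5.2.c describes a short inventory that participants complete, "indicating their number of days using marijuana, other drugs, and alcohol during the previous week". That text places it at treatment visits; Table 8.1, row 5 ("5. Weekly Drug and Alcohol Use Inventory"), marks it at baseline as well. The Addiction Severity Index and the Drug and Alcohol Use Questionnaire are also given at baseline.

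**The concern.** A day of any substance use can be a cannabis day, a drinking day or a day on another drug. Pre-treatment cannabis days are the baseline of one component only. Two features of this trial could make that covariate weak for the wider count:

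- Section 8.2.1.c stratifies by daily versus non-daily cannabis use over the past 30 days. Among daily users the covariate is close to 30 of 30, so it cannot separate drinkers from non-drinkers.
- Treatment is meant to reduce cannabis use. As cannabis days fall, more of the remaining use days come from alcohol and other drugs, for which the model holds no baseline.

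Section 9.4 excludes dependence on alcohol or other drugs, not their use, and section 8.4 schedules weekly toxicology and blood alcohol tests, so some use is foreseen. At stake is precision: with a target of 30 completers per group, the effect on any-substance days may be estimated with more noise than necessary, and a chance difference between groups in baseline drinking would go unadjusted.

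**Working it through.** **1. The plan's own figure.** Section 8.2 gives 60 completers, 30 per group, with no alpha, power, effect size or SD, so there is no power calculation to reproduce. For scale, with an assumed two-sided alpha of 0.05 and 80% power, the detectable standardised difference is (1.960 + 0.842) × √(2/30) = 0.72.

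**2. Which counts are affected.**

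| Outcome | Does the cannabis covariate carry its baseline? |
|---|---|
| Days of cannabis use | Yes |
| Days abstinent from cannabis | Yes: over a fixed 30-day window, abstinent days = 30 − cannabis days |
| Days of any substance use | Only in part |
| Days abstinent from all substances | Only in part, as for any-substance days |

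For abstinence from cannabis, fitting the model with x and then with 30 − x gave the same result (in one simulated trial, log rate ratio 0.0910 and SE 0.1052 both ways). The gain is zero.

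**3. Approximate formula for any-substance days.** Let r_own be the correlation of the outcome with its own baseline, and r_bb the correlation between baseline cannabis days and baseline any-substance days. If cannabis days predict the outcome only through its own baseline, the variance with own baseline relative to cannabis baseline is (1 − r_own²) / (1 − (r_own × r_bb)²). Both correlations are assumed.

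- r_own 0.3, r_bb 0.95: 0.91 / 0.9188 = 0.99
- r_own 0.5, r_bb 0.7: 0.75 / 0.8775 = 0.85
- r_own 0.7, r_bb 0.3: 0.51 / 0.9559 = 0.53

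Over r_own 0.3 to 0.7 and r_bb 0.3 to 0.95, the reduction is 1% to 47%.

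**4. Simulation with a 30-day baseline.** There were 60 participants and 70 treatment days, analysed by Poisson regression with a Pearson scale, since section 8.9 expects overdispersion. The entries compare a model with cannabis days plus baseline any-substance days against one with cannabis days alone. The share of daily users and the daily probability of other-substance use are assumed.

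| Daily users | Other use per day | Variance ratio |
|---|---|---|
| 30% | 3% | 0.92 |
| 30% | 10% | 0.75 |
| 30% | 30% | 0.58 |
| 70% | 3% | 0.94 |
| 70% | 10% | 0.79 |
| 70% | 30% | 0.63 |

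This simulation does not impose the restriction in step 3, so the two need not agree at a given correlation.

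**5. Simulation with the one-week window of the inventory.** This is closest to what the trial collects. Assumptions: 30–70% daily cannabis users, mean alcohol use 1.2–2 days a week, 60–90% of a person's drinking propensity carried over from baseline, and a mean cannabis reduction of 30–70%. Adding one week of other-substance days to cannabis days gave variance ratios of 0.59 to 1.01 over 36 scenarios. With a 30-day other-substance baseline they were 0.56 to 0.96 over 18 scenarios. The gain was near zero when most participants used daily and changed little, and largest when cannabis use fell most.

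**6. In participants.** A variance ratio v is worth 60 × (1/v − 1) extra participants: v = 0.95 gives 3, v = 0.75 gives 20, v = 0.59 gives 42, and v = 1 gives none.

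**7. Chance imbalance.** The SE of a baseline difference is √(2/30) = 0.258 SD. A difference of at least 0.3 SD (0.3/0.258 = 1.16 SE) arises by chance in about 25% of trials.

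**The case against.** The planned covariate is defensible. Cannabis days are part of any-substance days, so they are prognostic, and they match the stratification factor. The model sentence may be shorthand written around its lead outcome. The mood models concern other outcomes, so their different covariate is not a contradiction. Section 8.1 calls this a pilot feasibility study, and these outcomes are secondary and partly exploratory. The ASI alcohol and drug composites are analysed separately. The excluded dependence diagnoses limit heavy other-substance use, and the size of any gain rests entirely on assumed inputs that include no gain at all.

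These arguments limit the size and importance of the point, and they stand. They do not put baseline alcohol or other-drug use into the model.

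Three stronger readings are tempting and not supported:

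- *That the abstinence model also lacks its baseline.* This holds only if abstinence is from all substances. Section 8.9 leaves that open, and the urine definition points to cannabis.
- *That the comparison is biased.* It is not. Under randomisation, a chance imbalance in drinking is random error that a correctly estimated SE already covers.
- *That the exact baseline of any-substance days is already in hand.* The inventory is described as giving separate counts for marijuana, other drugs and alcohol over one week. Days with any use are the union of these and cannot be recovered exactly when substances overlap. Section 8.5.2.b describes the timeline follow-back for cannabis use data only.

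**Conclusion.** The point holds for days of any substance use, and for days of abstinence only if that means abstinence from all substances. It is a matter of efficiency on secondary outcomes: the primary outcome and the validity of the comparison are untouched. Under the assumptions above, the variance reduction from information like that in the baseline inventory runs from about 0 to 40%. Where in that range this trial would fall depends on how much participants drink or use other drugs, how stable that is, and how far cannabis use falls. The documents give none of these. The change is still worth making because it is nearly free, and because fixing the covariates before unblinding avoids a post hoc choice.

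**What to change.** Amend section 8.9 along these lines:

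> Days of abstinence are days without [state: cannabis, or any substance]. Models for days of cannabis use and days abstinent from cannabis adjust for pre-treatment days of cannabis use as the only use covariate. Models for days of any substance use, and for days abstinent from all substances if analysed, adjust for pre-treatment days of cannabis use and also for days of alcohol use and days of other-drug use in the week covered by the baseline inventory, each entered as log(days + 1).

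The added 1 handles zero counts. Separate alcohol and other-drug terms (two degrees of freedom) avoid double-counting days on which both were used; a single summed term (one degree of freedom) is acceptable if the overlap is acknowledged. Either is an imperfect proxy for the outcome's exact baseline. Section 8.9 should also state the window for pre-treatment cannabis days, and section 8.5.2.c should confirm that the inventory is given at baseline, as Table 8.1 shows. The cost is a short edit, one or two degrees of freedom, and no new data.

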**8. Research and Design Methods:**

**8.1. Overview**

We will conduct a Stage 1 pilot feasibility study at McLean Hospital to develop a medication to treat cannabis dependence. (FIGURE 1) In a randomized, double-blind, placebo-controlled trial, 60 cannabis-dependent subjects ages 18-45 will receive medical management (MM) over a 10-week period, with half receiving nabilone treatment and half receiving placebo. Participants will receive either 6 mg nabilone or placebo in addition to medical management (MM) over a 10-week treatment period.

**McLean Hospital Application to the Institutional Review Board (IRB)  
Nabilone for Cannabis Dependence Detailed Protocol**

Following treatment completion, participants will have a follow-up visits at 11, 12, 13, and 14 weeks. Primary outcomes will include self-report of cannabis smoking and results of quantitative urine drug screens for cannabis. We also will assess craving and other marijuana withdrawal symptoms as secondary measures. Mixed models ANOVA will be used to analyze the data.

The protocol described in this document has been approved by the FDA under IND 107862 to [name].

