## **8.2. Participants**

Male and female participants (ages 18-45) will be recruited from the Boston metropolitan area via websites, newspaper advertisements, flyers, and word-of-mouth. In order to meet our target sample of 60 study completers- (participants who complete all study procedures), we expect to recruit about 120 participants and have 90 sign the informed consent form . (Our target sample size is 60 completers with 30 per group: 30 Placebo and 30 Nabilone). From ongoing studies of cannabis smokers at McLean, we expect to recruit at least 3 participants a month for our study.

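### Section 8.9 states no baseline adjustment for the ASI mixed model; on its usual reading this loses precision, by an amount that depends on variance components the documents do not give

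*Combined protocol and SAP*

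**What the plan says.** Section 8.5.2.c schedules the ASI: severity "will be assessed at baseline and weeks 4, 10, and 14 with the Addiction Severity Index". Table 8.1 agrees. Section 8.9 then plans linear mixed models to "examine the effect of treatment group on changes in the ASI Drug and Alcohol composite scores during treatment and post-treatment follow-up assessments", with the effect judged "as determined by the group-by-time interaction in the linear mixed effects regression models". On covariance it says: "The linear mixed effects model will include random intercepts and slopes to appropriately account for correlation among repeated measures". The software is PROC MIXED.

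For this model, 8.9 does not say whether baseline ASI is a response, a covariate or left out. Nor does it say whether a group main effect is fitted, or whether time is linear or categorical. No ASI standard deviation, correlation or variance component appears anywhere.

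The neighbouring models are explicit. Days of use are adjusted for pre-treatment frequency. For mood episodes, "the logistic regression model will include the effects of treatment condition and the baseline measure of the outcome".

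The trial is randomised (8.1), and section 8.2 gives the size: "Our target sample size is 60 completers with 30 per group: 30 Placebo and 30 Nabilone".

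**The concern.** A group-by-time mixed model for a change from baseline is usually fitted with group, time and their product, and with the baseline value as the first repeated measure. The group main effect then lets the arms have different baseline means. In a randomised trial that difference is zero in expectation, so the parameter carries no treatment information. Estimating it lets a chance imbalance at baseline feed into the slope difference, much as in a change-score analysis. The estimate stays unbiased but is noisier than it needs to be.

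At stake is precision on the ASI composites, which are secondary measures in a pilot with 30 completers per arm and three post-baseline assessments. The loss arises with either coding of time, and no reason is given for treating the ASI differently from the adjacent outcomes.

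**Working it through.** The plan states no variance or power figure for the ASI, so there is nothing of its own to reproduce. The check compares the variance of the group-by-time coefficient with the group main effect free and with it fixed at zero.

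**Inputs from the documents.** Visits at t = 0, 4, 10 and 14 weeks (8.5.2.c); random intercept and slope (8.9); 30 per arm (8.2), which cancels from the ratio.

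**Assumed inputs.** Complete data and linear time. Total baseline variance is 1, made up of the intercept variance (equal to the intraclass correlation, ICC: 0.3, 0.5, 0.7) and the residual variance σ² = 1 - ICC. Slope variance d is 0.0005, 0.001 or 0.003 per week squared. The intercept-slope correlation is 0 at first, then varied.

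**Formula.** With all visits observed, each participant's fitted intercept and slope have covariance D + σ²(Z'Z)⁻¹, where D is the random-effects covariance matrix. Σt = 28 and Σt² = 16 + 100 + 196 = 312. The determinant of Z'Z is 4 × 312 - 28² = 464. So (Z'Z)⁻¹ has entries 312/464 = 0.6724 (intercept), 4/464 = 0.00862 (slope) and -28/464 = -0.0603 (covariance). Let r be the resulting correlation between the estimated intercept and slope differences. Fixing the baseline difference at zero multiplies the slope variance by 1 - r².

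**Worked case, ICC 0.5, d = 0.001, correlation 0.**
- Intercept: 0.5 + 0.5 × 0.6724 = 0.8362
- Slope: 0.001 + 0.5 × 0.00862 = 0.00531
- Covariance: -0.5 × 0.0603 = -0.0302
- r² = 0.000910 / (0.8362 × 0.00531) = 0.205, so the ratio is 0.795

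**Ratio of constrained to unconstrained variance, correlation 0.**

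| ICC | d = 0.0005 | d = 0.001 | d = 0.003 |
|---|---|---|---|
| 0.3 | 0.646 | 0.671 | 0.744 |
| 0.5 | 0.774 | 0.795 | 0.851 |
| 0.7 | 0.882 | 0.899 | 0.935 |

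The reduction is 1 - 0.935 = 6.5% to 1 - 0.646 = 35.4%. Expressed as inflation from leaving the term free, the same table gives 1/0.935 = 1.07 to 1/0.646 = 1.55.

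**Intercept-slope correlation varied from -0.5 to +0.3, same grid.**
- Largest gain (ICC 0.3, d = 0.001, correlation -0.5): the covariance becomes -0.0422 - 0.0087 = -0.0509. Then r² = 0.002591 / (0.7707 × 0.007034) = 0.478, so the ratio is 0.52.
- Smallest gain (ICC 0.7, d = 0.003, correlation +0.3): the covariance becomes -0.0181 + 0.0137 = -0.0044. Then r² = 0.000019 / (0.9017 × 0.005586) = 0.004, so the ratio is 0.996.

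**Categorical time, week 10 against baseline, correlation 0.** The ratio is (V₁₀ - C²) / (V₁₀ + 1 - 2C), with V₁₀ = 1 + 100d and C = ICC. At ICC 0.3 and d = 0.0005: 0.96/1.45 = 0.66. At ICC 0.7 and d = 0.003: 0.81/0.90 = 0.90.

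**Baseline as covariate, with the test left on the interaction.** Weeks 4, 10 and 14 alone give a sum of squares about the mean time of 312 - 28²/3 = 50.67, against 312 - 28²/4 = 116 for four visits. The slope variance is then (d + σ²/50.67) / (d + σ²/116) times that of the unconstrained four-visit model. This is 0.01432/0.00653 = 2.2 at ICC 0.3 and d = 0.0005, and 0.00892/0.00559 = 1.6 at ICC 0.7 and d = 0.003.

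**The case against.** The strongest reply is that 8.9 never says baseline is an unconstrained response. A model with time and group-by-time terms and no group main effect is also judged by the interaction, so the text is compatible with the better model. The phrase about assessments during treatment and follow-up could also mean weeks 4, 10 and 14 only. This stands: the model form is inferred. A reader might take the plan to specify a free baseline difference, and the documents do not support that. The other reading does not rescue the plan, however. An interaction over weeks 4 to 14 would miss a group difference already fully present at week 4, and baseline would go unused.

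A second reply is that an unconstrained group-by-time model is standard and valid, and that the ASI is secondary in a pilot whose outcomes are exploratory. This also stands. It limits the priority but gives no reason to forgo the precision.

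A third reply is that equal baseline means are guaranteed only for all randomised participants, while 8.9 also replicates every analysis in completers, who are selected after randomisation. This is correct and shapes the fix.

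**Conclusion.** The point holds as a gap in specification with a likely cost in precision. On the usual reading, the ASI analysis spends information on a baseline difference that is zero in expectation. With ICC 0.3 to 0.7, slope variance 0.0005 to 0.003, complete data and uncorrelated random intercepts and slopes, constraining the baseline cuts the slope-contrast variance by about 7% to 35%. If the intercept-slope correlation may lie between -0.5 and +0.3, the cut is anywhere from under 1% to about 48%.

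A reader might infer that 7% to 35% is a property of this plan, or that the planned analysis is biased. Neither follows: the variance components are assumptions, and only precision is affected. The direction is firmer than the size, since the unconstrained variance is never the smaller of the two when the baseline means are equal. Minor priority.

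**What to change.** In 8.9, state that for the intent-to-treat analysis the ASI model takes baseline and weeks 4, 10 and 14 as responses with a common baseline mean: time and group-by-time terms, no group main effect. Keep the random effects and PROC MIXED.

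If the sponsor prefers to model weeks 4, 10 and 14 with baseline ASI as a covariate, name the group effect or visit-specific group contrasts as the test. The group-by-time interaction should not be the test in that form.

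For the completers-only replication, enter baseline as a covariate, or note the common baseline mean as an assumption.

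The cost is a few sentences in 8.9 and a small change to the model statement. No new data or participants are needed.

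### Mood is analysed only as undefined yes/no episodes built from symptom and affect scales; the scores themselves should carry the main mood analysis

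*Combined protocol and SAP*

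**What the plan says.** The mood paragraph of Section 8.9 names the outcome and its sources: "mood episodes will be assessed during treatment and post-treatment follow-up, using the QIDS, BAI, and PANAS". It then sets the model: "changes in risk of mood episodes during treatment and post-treatment follow-up assessments will be analyzed via a logistic regression model". The fit is by GEE, "to account for correlation among repeated binary outcomes on the same individual". For the effect of nabilone, "the logistic regression model will include the effects of treatment condition and the baseline measure of the outcome". The paragraph likens this model to a logistic model earlier in the section. Section 8.9 plans no analysis of the mood scores as scores.

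Section 8.5.3 describes the three instruments:

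- the BAI is a 21-"item self-report measure that can be used to assess the severity of anxiety";
- the QIDS "is a short self-report questionnaire for depressive symptoms used successfully in the STAR\*D project";
- the PANAS is a "20-item self-report scale in which mood variables are rated by participants on a 1-5 scale".

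Table 8.1 schedules all three at baseline, weeks 4 and 10, and week 14. The SCID is scheduled at baseline only. The ASI has the same schedule as the mood scales, and its composites stay as scores: "Linear mixed effects models will be used to examine the effect of treatment group on changes in the ASI Drug and Alcohol composite scores". That model has random intercepts and slopes and tests the group-by-time interaction.

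**The concern.** No instrument used after baseline diagnoses a mood episode, so the outcome has to be made by cutting scores. The plan does not say where each scale is cut, whether one scale or several must cross, or whether the result is one outcome or three. Those choices could be made after the data are seen.

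Cutting also discards information, in a trial that aims for only 60 completers. A mood difference in either direction becomes easier to miss, and the answer comes to depend on the cut. The same section keeps the ASI composites as scores and gives no reason for treating mood differently.

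The text speaks of changing risk during treatment and follow-up, but the listed terms would give one average treatment effect over visits on and off drug. An effect present only on drug would be diluted by week 14.

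**Working it through.** **Plan's own figure.** There is none to reproduce. Sections 8.2 and 9.1 give recruitment numbers only, with no alpha, power, effect size, SD or episode rate for any outcome.

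**Inputs from the documents.** 30 completers per arm (Section 8.2); post-baseline mood visits at weeks 4, 10 and 14 (Table 8.1).

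**Assumed inputs.** Approximately normal scores; two-sided alpha 0.05; episode share p from 10% to 50%; between-visit correlation 0.5 or 0.7; baseline correlation 0.3 to 0.7.

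**1. Is an episode defined?** No. Section 8.5.3 gives no cut-off and Section 8.9 gives no rule. The logistic model that the mood paragraph points back to is not there: the text before it specifies a GEE for urine screens with no link named, a Poisson or log-linear model, and linear mixed models.

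**2. Information kept at one assessment.** For a normal score cut so that a share p counts as an episode, with c = z(1−p), relative efficiency is φ(c)² / [p(1−p)].

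- p = 0.50: 0.3989² / 0.25 = 0.637
- p = 0.10: 0.1755² / 0.09 = 0.342

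| Episode share | Kept | Lost | Effective n of 60 |
|---|---|---|---|
| 50% | 0.637 | 36% | 38 |
| 30% | 0.576 | 42% | 35 |
| 20% | 0.490 | 51% | 29 |
| 10% | 0.342 | 66% | 21 |

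The loss reaches 50% at a share of about 21%.

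**3. Three visits combined.** Compare the mean of three scores with the mean of three yes/no indicators. The ratio in step 2 is multiplied by (1+2r)/(1+2k), where r is the correlation between scores and k the correlation it implies between indicators. For p = 0.10 and r = 0.5, k = 0.249, so 0.342 × 2 / 1.498 = 0.457. Over both values of r the loss is 54–55% at a 10% share, 38% at 20%, 29–30% at 30% and 23–24% at 50%.

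**4. Baseline adjustment.** If baseline is split at its median as well, efficiency at one visit is (2/π)(1−ρ²)/(1−k²), with k = (2/π)·arcsin ρ. For ρ = 0.3, 0.5 and 0.7 this gives 0.602, 0.537 and 0.429, so losses of 40%, 46% and 57%.

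**5. What this does to power at one visit.** With 30 per arm, the difference detectable with 80% power on the score is (1.960 + 0.842) × √(2/30) = 0.72 SD. At 0.735 SD, power is Φ(0.735 × √15 − 1.960) = Φ(0.887) = 81%. For the same shift after cutting, with q the mean of the two rates:

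power = Φ{ [|p₁−p₂| − 1.960·√(2q(1−q)/n)] / √([p₁(1−p₁)+p₂(1−p₂)]/n) }

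| Placebo rate | Nabilone rate if lower / higher | Power if lower / higher |
|---|---|---|
| 10% | 2.2% / 29.2% | 24% / 47% |
| 20% | 5.7% / 45.8% | 38% / 57% |
| 30% | 10.4% / 58.3% | 47% / 60% |
| 50% | 23.1% / 76.9% | 58% / 58% |

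**6. Model terms.** Treatment and baseline are listed; time and treatment-by-time are not. Section 8.2.1.e ends treatment at 10 weeks, so week 14 is off drug. Under Section 8.3.1.b, 1 + 1 + 1 + 6 = 9 weeks precede the taper, so week 10 is the taper week. The three visits therefore represent different exposure.

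**The case against.** The strongest defence is that this is a Stage 1 pilot. Neither aim in Section 5 concerns mood, the mood analyses are secondary, and no outcome has a power target, so a power comparison carries little weight. A yes/no state can be easier to interpret clinically. The planned analysis uses repeated visits, for which single-visit losses overstate the cost. The intent-to-treat set may exceed 30 per arm. The listed terms need not be exhaustive, and a baseline-adjusted treatment effect is a legitimate way to address change. The logistic model referred to may simply be the urine-screen GEE.

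Much of this stands. It limits the consequence to a secondary outcome and makes the power figures illustrations. It does not supply an episode definition or a reason to avoid the scores. If the urine-screen GEE is meant, its terms are not given either, so the reference does not fill the gap.

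Three stronger readings are tempting:

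- **At least half the information is lost.** The documents do not support this. Without baseline adjustment, one visit loses that much only at a share of about 21% or less; with three visits the crossing lies between 10% and 20%. With a split baseline it can also happen at a median split, but only at a high assumed correlation (57% at 0.7, 46% at 0.5).
- **Events will be few and the logistic model unstable.** Section 9.4 excludes serious psychiatric disorder, not raised symptom scores, and an unstated cut could be crossed often. The 10% scenario with more episodes on nabilone implies about 3 against 9 events per visit (30 × 0.10 and 30 × 0.292). Instability has not been shown.
- **A mood safety signal would be missed.** Safety does not rest on this model. Table 8.1 has the C-SSRS and adverse events weekly, and Section 8.2.1.a has the physician assess suicide risk at each medical management visit.

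**Conclusion.** The point holds as a recommended change to a secondary analysis. Three facts come from the documents alone: mood is analysed only as a yes/no episode, nothing defines the episode, and the listed terms leave out time while combining on-treatment and follow-up visits.

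The size depends on assumptions. Under approximate normality, the loss is about one third (median split) to two thirds (10% share) at one assessment, and about 23% to 55% with three visits combined. The three-visit range further assumes the same shift at each visit and no baseline adjustment. Since the plan gives neither cut-off nor rate, no single figure can be fixed. The direction does not depend on the rate: scores were more efficient at every share checked. Marked skewness would weaken that comparison.

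**What to change.** Replace the mood paragraph of Section 8.9 with the following content:

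- **Main mood analysis.** QIDS, BAI, PANAS-positive and PANAS-negative scores, each in a linear mixed model over weeks 4, 10 and 14 with baseline score, treatment, time and treatment-by-time, in all randomised participants. Section 8.5.3 should state how the two PANAS scores are formed.
- **Key contrast.** Name one per outcome. An example is the nabilone–placebo difference averaged over weeks 4 and 10, with week 14 shown separately; the choice should recognise that week 10 is the taper week. Label the four outcomes exploratory.
- **Episodes.** Supportive or descriptive only, with the threshold for each scale and the combining rule fixed before unblinding. Remove or complete the reference to an earlier logistic model.
- **Check.** Inspect the scores for skewness and state in advance what will be done if it is marked.

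The model resembles the planned ASI model and can use PROC MIXED, but it is not identical: the ASI model lists no baseline covariate. No new data are needed. The cost is SAP wording, slightly more analysis work, a distribution check, and four secondary outcomes in place of what reads as one. The primary analysis does not change.
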